10.3.4.2.3 Physical Examination

A complete physical examination excluding the genitourinary examination will be performed at Screening, while limited physical examinations (to include HEENT, cardiorespiratory, abdomen, and range of motion) will be performed as indicated in the Schedule of Events (Section 2.2).

10.3.4.2.4 Other Safety Variables

Local tolerability will be assessed on a 0-3 scale (none, mild, moderate, severe). All application site reactions will be recorded as TEAEs in the diary. These should include the date and severity of the TEAE.

10.3.4.3 Adverse Events

The definitions and management of AEs, and any special considerations for AEs, are provided in Section 11.

10.4. Procedural Adjustments Due to COVID-19

The coronavirus (COVID-19) global pandemic has impacted the free movement of the world's population, which has been restricted to control the spread of the disease. It is recommended that all sites and subjects comply with the applicable local and federal guidelines regarding the necessary and proper precautions regarding COVID-19.

Although it is preferable to conduct all necessary study assessments in person (onsite visits), this may not be possible as a result of COVID-19-related travel restrictions. To ensure the safety of subjects, investigators, and site staff, Visits 3-6 (Double-blind Period; [Table 2-1](#)), Visits 7-11 (OLE Period; [Table 2-2](#)) and unscheduled visits may be conducted remotely. Screening and baseline visits must be performed onsite only, and must be postponed or scheduled for when onsite visits can be safely conducted.

[Appendix B](#) details the procedures when it is inadvisable or not possible to conduct an onsite study visit.

11. ADVERSE EVENTS

11.1. Definitions

11.1.1 Adverse Events

An AE is defined as any untoward medical occurrence in a patient or clinical investigation subject administered a pharmaceutical product that does not necessarily have a causal relationship with this treatment. An AE can therefore be any unfavorable and unintended sign (including an abnormal laboratory finding, for example), symptom, or disease temporally associated with the use of a medicinal product, whether or not related to the medicinal product.

Pre-existing diseases or conditions will not be considered AEs unless there is an increase in the frequency or severity, or a change in the quality, of the disease or condition. (Worsening of a pre-existing condition is considered an AE.)

Events that occur in subjects treated with control product are also considered AEs.

11.1.2 Adverse Drug Reaction

All noxious and unintended responses to an investigational product related to any dose should be considered adverse drug reactions (ADRs).

The phrase “responses to an investigational product” means that a causal relationship between an investigational product and an AE is at least a reasonable possibility, i.e., the relationship cannot be ruled out. All AEs judged by either the reporting investigator or the sponsor as having a reasonable causal relationship to an IP qualify as ADRs.

All AEs for which the judgment of relationship to IP is “possible” or higher will be considered ADRs. If a relationship to IP is not provided, then the AE must be treated as if it were “possible.”

11.1.3 Unexpected Adverse Event/Adverse Drug Reaction

An expected AE or ADR is one for which the nature or severity is consistent with the known AE profile of the product. For a preapproval test product, the known information is contained in the IB. For a marketed product, the known information is contained in the current package insert for the product.

An unexpected adverse event (UAE) or unexpected adverse drug reaction (UADR) is one for which the nature or severity of which is not consistent with the applicable product information (e.g., Investigator’s Brochure [IB] for an unapproved investigational product or package insert/summary of product characteristics for an approved product). For example, hepatic necrosis would be unexpected (greater severity) if the IB only listed elevated hepatic enzymes or hepatitis.

Likewise, cerebral thromboembolism and cerebral vasculitis would be unexpected (greater specificity) if the IB only listed cerebral vascular accidents.

Furthermore, reports that add significant information on specificity or severity of a known, already documented adverse reaction constitute unexpected events.

11.1.4 Serious Adverse Events/Drug Reaction

A serious adverse event (SAE) is any untoward medical occurrence that at any dose:

- results in death
- is life-threatening
NOTE: The term “life-threatening” in the definition of “serious” refers to an event in which the subject was at risk of death at the time of the event; it does not refer to an event that hypothetically might have caused death if it were more severe.
- requires inpatient hospitalization or prolongation of existing hospitalization
NOTE: Inpatient hospitalization is defined as 24 hours in a hospital or an overnight stay. An elective hospital admission to treat a condition present before exposure to the IP, or a hospital admission for a diagnostic evaluation of an AE, does not qualify the condition or event as an SAE. Further, an overnight stay in the hospital that is only due to transportation, organization, or accommodation problems and without medical background does not need to be considered an SAE.
- results in persistent or significant disability/incapacity
- is a congenital anomaly
NOTE: A congenital anomaly in an infant born to a mother who was exposed to the IP during pregnancy is an SAE. However, a newly diagnosed pregnancy in a subject that has received an IP is not considered an SAE unless it is suspected that the IP(s) interacted with a contraceptive method and led to the pregnancy.
- is an important medical event
NOTE: Medical and scientific judgment should be exercised in deciding whether it is appropriate to consider other situations serious, such as important medical events that may not be immediately life-threatening or result in death or hospitalization but may jeopardize the subject or may require intervention to prevent one of the other outcomes listed in the definition above. Examples of such events are intensive treatment in an emergency room or at home for allergic bronchospasm, blood dyscrasias, or convulsions that do not result in hospitalization, development of drug dependency, or drug abuse. The occurrence of malignant tumors is also to be considered serious.

11.1.5 Significant Adverse Events

Other significant AEs are defined as marked hematological and other laboratory abnormalities (other than those meeting the definition of serious) and any events that led to an intervention, including withdrawal of test drug, dose reduction, or significant additional concomitant therapy.

11.1.6 Treatment-Emergent Adverse Events

An AE is defined as treatment emergent if the first onset or worsening is after the first application of IP (trifarotene or vehicle) and not more than 14 days after the last application of IP.

11.2. Event Assessment and Follow-up of Adverse Events

The occurrence of an AE or SAE may come to the attention of study personnel during study visits and interviews of a study participant presenting for medical care or upon review by a study monitor.

All reported AEs, including local and systemic AEs not meeting the criteria for SAEs, will be captured on the appropriate eCRF. Information to be collected includes event description, time of onset, clinician's assessment of severity, relationship to study product (assessed only by those with the training and authority to make a diagnosis), and time of resolution/stabilization of the event. All reported AEs occurring while on study must be documented appropriately regardless of relationship. All reported AEs will be followed to adequate resolution.

Any medical condition that is present at the time that the participant is screened will be considered as baseline and not reported as an AE. However, if the study participant's condition deteriorates at any time during the study, it will be recorded as an AE.

Changes in the severity of a reported AE will be documented to allow an assessment of the duration of the event at each level of severity to be performed. AEs characterized as intermittent require documentation of onset and duration of each episode.

Study clinic personnel will record all reportable events with start dates occurring any time after informed consent is obtained until 14 (for nonserious AEs) or 30 days (for SAEs) after the last day of study participation. At each study visit, the investigator will inquire about the occurrence of AE/SAEs since the last visit. Events will be followed for outcome information until resolution or stabilization.

11.2.1 Assessment

The investigator is responsible for the detection and documentation of events meeting the criteria and definition of an AE or SAE described previously. At each visit, the subject will be allowed time to spontaneously report any issues since the last visit or evaluation. The investigator will then monitor and/or ask about or evaluate AEs using nonleading questions, such as

- “How are you feeling?”
- “Have you experienced any issues since your last visit?”
- “Have you taken any new medications since your last visit?”

Any clinically relevant observations made during the visit will also be considered AEs. In addition, although local tolerability will be assessed on a 0-3 scale, all application site reactions should be recorded as AEs.

The Tolerability Assessments Form at each visit collects a numeric severity score by body area for erythema, stinging/burning, and pruritus.

In addition, if skin irritation is more than the expected erythema, stinging/burning, and pruritus with the application of this topical retinoid (i.e., clinically relevant), please enter the application site reactions in the Adverse Event description section. If a diagnosis is known, record the diagnosis. If a diagnosis is known and there are other signs/symptoms that are not generally part of the main diagnosis, record the diagnosis and each sign/symptom on a separate line. If a diagnosis is not known, record each sign/symptom on a separate line. Examples are allergic contact dermatitis, sunburn, skin erosion, and swelling.

11.2.2 Evaluation

11.2.2.1 Severity of Adverse Events

The clinical severity of an AE will be classified as follows:

Mild	Usually transient and may require only minimal treatment or therapeutic intervention. The event does not generally interfere with usual activities of daily living.
Moderate	Usually alleviated with additional specific therapeutic intervention. The event interferes with usual activities of daily living, causing discomfort but poses no significant or permanent risk of harm to the subject.
Severe	Interrupts usual activities of daily living, or significantly affects clinical status, or may require intensive therapeutic intervention.

It is important to distinguish between severe AEs and SAEs. Severity is a classification of intensity whereas an SAE is an AE that meets serious criteria, as described in Section 11.1.4.

11.2.2.2 Seriousness

The investigator is to evaluate whether the AE meets serious criteria, as described in Section 11.1.4.

11.2.2.3 Action(s) Taken

All AEs will be treated/managed according to standard practice. The following actions may be taken with regard to the IP. Section 9.4 describes dose adjustment and stopping rules for individual subjects.

Action(s) taken may consist of the following:

Dose not changed	An indication that a medication schedule was maintained.
Dose reduced	An indication that a medication schedule was modified by reducing the frequency of application.
Drug interrupted	An indication that a medication schedule was modified by temporarily terminating a prescribed regimen of medication.
Drug withdrawn	An indication that a medication schedule was modified through termination of a prescribed regimen of medication.
Not applicable	Determination of a value is not relevant in the current context.
Unknown	Not known, not observed, not recorded, or refused.

11.2.2.4 Outcome at the Time of Last Observation

The outcome of an AE at the time of last observation will be classified as follows:

- Recovered/resolved
- Recovered/resolved with sequelae
- Recovering/resolving
- Not recovered/not resolved
- Fatal*
- Unknown

*Only select fatal as an outcome when the AE results in death. If more than one AE is judged to be possibly related to the subject's death, the outcome of death should be indicated for each such AE. Although "fatal" is usually an event outcome, events such as sudden death or unexplained death should be reported as SAEs.

11.2.2.5 Adverse Event Relationship to Investigational Product

The investigator must make an assessment of each AE's relationship to the IP. The categories for classifying the investigator's opinion of the relationship are as follows:

Not related	An AE with sufficient evidence to accept that there is no causal relationship to IP administration (e.g., no temporal relationship to drug administration, because the drug was administered after onset of event; investigation shows that the drug was not administered; another cause was proven.)
Unlikely related	An AE, including laboratory test abnormality, with a temporal relationship to IP administration that makes a causal relationship improbable, and in which other drugs, events, or underlying disease provide plausible explanations.
Possibly related	An AE with a reasonable time sequence to administration of the IP, but that could also be explained by concurrent disease or other drugs or events. Information on drug withdrawal may be lacking or unclear.
Related	An AE occurring in a causal plausible time relationship to IP administration that cannot be attributed to a concurrent disease or other drugs, chemicals, or events. The AE relationship to the IP must be assessed separately by the investigator and Mayne Pharma LLC.

11.2.3 Documentation

Any AE that occurs during the Screening Period will be captured as on the AE page of the eCRF (not medical history). All AEs that occur within the period of observation for the study must be documented in the eCRF with the following information, where appropriate. (The period of observation for the study is described in Section 11.2.)

- AE name or term
- When the AE first occurred (start date and time)

- When the AE stopped (stop date and time or an indication of “ongoing”)
- Severity of the AE
- Seriousness (hospitalization, death, etc.)
- Actions taken
- Outcome
- Investigator opinion regarding the AE relationship to the IP(s)

11.2.4 Treatment of Adverse Events

Adverse events that occur during the study will be treated, if necessary, by established standards of care. If such treatment constitutes a deviation from the protocol, the subject may be withdrawn for treatment but continue to be followed for efficacy and safety in the study. The decision about whether the subject may continue in the study will be made by the sponsor after consultation with the investigator and/or medical monitor.

If AEs occur in a subject that are not tolerable, the investigator must decide whether to stop the subject’s involvement in the study and/or treat the subject. Special procedures may be recommended for the specific IP, such as the collection of a serum sample for determining blood concentrations of IP, specific tapering procedures, or treatment regimens, as appropriate.

It is not necessary to unblind a subject’s treatment assignment in most circumstances, even if an SAE has occurred. If unblinding is necessary, see Section 9.6 for a description of the unblinding procedures.

11.2.5 Follow-up

Any AE will be followed (up to a maximum of 14 days after the last dose of IP) to a satisfactory resolution, until it becomes stable, or until it can be explained by another known cause(s) (i.e., concurrent condition or medication) and clinical judgment indicates that further evaluation is not warranted. All findings relevant to the final outcome of an AE must be reported in the subject’s medical record and recorded on the eCRF page.

11.2.6 Reporting

11.2.6.1 Serious Adverse Events

The investigator or designee must report all SAEs promptly to Premier Research within 24 hours of first becoming aware of the event by e.g., completing, signing and dating the Serious Adverse Event Report Form, verifying the accuracy of the information recorded in the form with the source documents and eCRF, and sending the SAE form to the Premier Research by one of the following methods:

Email: [contact]

Email: [contact]

[contact]

[contact]

This written report should be submitted on the SAE form provided for this purpose. At the time of first notification, the investigator or designee should provide the following information, if available:

- Protocol number
- Reporter (study site and investigator)
- Suspect IP
- Subject's study number
- Subject's year of birth
- Subject's gender
- Date of first dose of IP(s)
- Date of last dose of IP(s), if applicable
- Adverse event term
- Date of occurrence of the event
- A brief description of the event, outcome to date, and any actions taken
- The seriousness criteria(on) that were met
- Concomitant medication at onset of the event
- Relevant medical history information
- Relevant laboratory test findings
- Investigator's opinion of the relationship to IP(s) ("Is there a reasonable possibility that the IP caused the SAE? Yes or No?")
- Whether and when the investigator was unblinded as to the subject's treatment assignment

Any missing or additional relevant follow-up information concerning the SAE should be sent to the sponsor/sponsor representative via the same contact details above as soon as possible on a follow-up SAE Report Form, together with the following minimal information (initial report, adverse event, date of occurrence, subject identification (ID), study ID, IP, and site number); this will allow the follow-up information to be linked to the initial SAE report.

Specific information may be requested by the Premier Research Pharmacovigilance Department using a follow-up request form or via email communication.

The investigator is required to comply with applicable regulations (including local laws and guidances) regarding the notification of his or her health authorities, institutional review board (IRB)/independent ethics committee (IEC), principal and coordinating investigators, study investigators, and institutions. Each investigator is obligated to learn about the reporting requirements for investigators in his/her country. The study monitor may be able to assist with this.

11.2.6.2 Adverse Drug Reactions

All ADRs should be reported by the investigator in the eCRF.

Suspected serious ADRs must be reported to the sponsor immediately, regardless of the time elapsed since the end of the observation period.

11.2.6.3 Nonserious Adverse Events

Nonserious AEs will be recorded in the eCRF and reported by Premier Research to Mayne Pharma LLC in aggregate monthly status reports.

11.3. Special Considerations

11.3.1 Adverse Events of Special Interest

Since topical retinoids are associated with local application site AEs, particularly when beginning treatment, these events will be followed closely during the study and considered AEs of special interest (AESIs).

11.3.2 Pregnancy

All WOCBP who participate in the study should be counseled on the need to practice highly effective birth control and on the importance of avoiding pregnancy during study participation. Women should be instructed to contact the investigator or study staff immediately if pregnancy occurs or is suspected.

Pregnancy testing will be conducted prior to administration of the IP on every woman of childbearing potential. A woman who is found to be pregnant at the Screening Visit will be excluded from the study and considered to be a screening failure.

A woman who becomes pregnant during IP treatment will be immediately discontinued from study treatment. The investigator must report the pregnancy of any woman who becomes pregnant during or within 30 days after discontinuing treatment as if it were an SAE within 24 hours of learning of the pregnancy, to Premier Research Pharmacovigilance using the Pregnancy Data Collection Form via the same fax number and/or email address as for SAE reporting. If a partner of a male study subject becomes pregnant, the investigator must report the pregnancy as soon as possible after learning of it to the Premier Research Pharmacovigilance using the Pregnancy Data Collection Form. A separate pregnant partner ICF will be required.

Early Termination Visit assessments are required as soon as possible after learning of the pregnancy in a study subject. The investigator is also responsible for following the pregnancy until delivery or termination. These findings must be reported on the Pregnancy Data Collection Form and forwarded to Premier Research Pharmacovigilance. The event meets the SAE criterion only if it results in a spontaneous abortion or a congenital anomaly. In such case, an additional form (Serious Adverse Event Report Form) must be filled out by the investigator and provided to Premier Research Pharmacovigilance within 24 hours of knowledge of the pregnancy's serious outcome.

Among the clinical studies, 12 pregnancies were reported: 4 resulted in normal births; 5 resulted in spontaneous abortions (none of which was considered related to CD5789); 1 was electively

aborted, and 2 were lost to follow-up (Investigator's Brochure for CD5789 Cutaneous Formulation).

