5.3. Summary of Potential Risks and Benefits

Although the primary objective of this study is safety in the patient population with LI, the potential benefits of study participation are that subjects with LI may experience a reduction in their LI symptoms as a result of treatment with trifarotene (CD5789) cream HE1. No other benefits of participation are anticipated.

The potential risks of study participation for all subjects include those associated with exposure to trifarotene (CD5789) cream HE1 and the risks of medical evaluation, including venipuncture. The study population will comprise adults and adolescents aged 12 to 17 years.

Animal studies with CD5789 have shown reproductive toxicity in the embryo-fetal studies. Despite low systemic levels with the CD5789 concentration of 50 µg/g used in patients with acne, CD5789 must not be administered during pregnancy.

When CD5789 is used in the other formulations and/or for other indications and/or with higher concentrations or higher application surface areas, the potential risk of teratogenicity needs to be considered as the safety margin may be lower. Depending on the study population and conditions mentioned above, or other specific requirements, the appropriate contraception method is described in this protocol.

It is unknown whether CD5789 or its metabolites are excreted in human milk. A risk to the newborns/infants cannot be excluded. Lactating women are not eligible for the clinical study.

Certain cutaneous signs and symptoms of irritation and localized reactions at the application site such as erythema, scaling, dryness, stinging/burning, and pruritus may be experienced with use of CD5789. Depending upon the severity of these side effects, subjects may be instructed to reduce the frequency of application or to discontinue use.

Trifarotene cream contains propylene glycol that is mildly irritant to the skin, eyes, and mucous membranes. Trifarotene (CD5789) cream HE1 also contains butylated hydroxytoluene that may cause local skin reactions (e.g., contact dermatitis), or irritation to the eyes and mucous membranes and sodium benzoate that is mildly irritant to the skin, eyes, and mucous membranes.

CD 5789 is mildly irritant to the skin, eyes, and mucous membranes. Therefore, it should not come into contact with the eyes, mouth, or mucous membranes.

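### Section 11.3.2 limits SAE status for pregnancy to two outcomes, which contradicts Section 11.1.4 and leaves other serious outcomes without a clear form or deadline

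*Protocol*

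**What the plan says.** Section 11.3.2 (Pregnancy) reads the same on this point in the Amendment 3 and Amendment 2 texts. It does four things.

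- It requires a pregnancy in a female subject, during treatment or within 30 days after stopping, to be reported "as if it were an SAE within 24 hours of learning of the pregnancy", on the Pregnancy Data Collection Form.
- It sets the length of follow-up: "The investigator is also responsible for following the pregnancy until delivery or termination". Findings go to pharmacovigilance on the same form.
- It limits SAE status: "The event meets the SAE criterion only if it results in a spontaneous abortion or a congenital anomaly".
- It attaches the SAE form to that limit: "In such case, an additional form (Serious Adverse Event Report Form) must be filled out by the investigator", within 24 hours of learning of the serious outcome.

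Section 11.1.4 gives the general definition: "A serious adverse event (SAE) is any untoward medical occurrence that at any dose" meets one of six criteria. These are death, threat to life, hospitalization ("requires inpatient hospitalization or prolongation of existing hospitalization"), disability, congenital anomaly, or an important medical event. Its note on pregnancy says that a newly diagnosed pregnancy "is not considered an SAE unless it is suspected that the IP(s) interacted with a contraceptive method and led to the pregnancy".

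Section 11.2.6.1 requires all SAEs to be reported within 24 hours of awareness and makes no exception for pregnancy.

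**The concern.** The same protocol defines seriousness for pregnancy twice, and the definitions differ. The words *only if* in 11.3.2 close the list at two outcomes, whereas 11.1.4 leaves it open to any serious occurrence and adds a trigger that 11.3.2 omits. Because 11.3.2 also decides when the SAE form is completed, the difference affects what a site does.

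What is at stake is uniform and prompt reporting of serious pregnancy outcomes for a product about which Section 5.3 says: "Animal studies with CD5789 have shown reproductive toxicity in the embryo-fetal studies". The trial enrols women of childbearing potential, and the Amendment 2 text also admits adolescents.

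**Working it through.** The protocol gives no figure to reproduce and no arithmetic applies. The check sets the two definitions side by side and then the deadlines.

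**Step 1: is it an SAE?**

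| Situation | Section 11.1.4 | Section 11.3.2, read as written | Agree? |
|---|---|---|---|
| Pregnancy with suspected product–contraceptive interaction, neither listed outcome | SAE (pregnancy note) | Not an SAE | No |
| Ectopic pregnancy treated as an inpatient | SAE (hospitalization) | Not an SAE | No |
| Life-threatening complication of pregnancy | SAE (threat to life) | Not an SAE | No |
| Congenital anomaly in an exposed infant | SAE (named) | SAE (named) | Yes |
| Spontaneous abortion | Not named; an SAE if it meets a general criterion | SAE (named) | Only in part |
| Uncomplicated pregnancy and normal birth | Not an SAE | Not an SAE | Yes |

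By name, the two lists share only congenital anomaly. The other five of the six criteria in 11.1.4 do not appear in the 11.3.2 list, and neither does the contraceptive-interaction trigger. The first row is a flat contradiction: one section says SAE, the other says not, about the same event.

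**Step 2: which form, and by when?**

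- Learning of a pregnancy in a female subject: pregnancy form, 24 hours (11.3.2).
- Spontaneous abortion or congenital anomaly: SAE form as well, 24 hours from knowing the outcome (11.3.2).
- Any other outcome under 11.3.2: pregnancy form only, no time stated.
- Any other outcome that is serious under 11.1.4: SAE report, 24 hours (11.2.6.1).

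The last two lines can describe the same event. No order of precedence between the sections is given, so two sites could each follow a section of the protocol faithfully and report that event differently.

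**Step 3: is this superseded text?** No. The sentence stands in the body of both amended protocols. The summaries of changes show that this paragraph was revised, with the limiting sentence kept and the sentence tying the SAE form to it included in the revision.

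**The case against.** The strongest reply is that *the event* in 11.3.2 means the pregnancy as such, which 11.1.4 also treats as generally not serious. On that reading a hospitalized complication is an untoward occurrence in its own right, 11.1.4 makes it an SAE, and 11.2.6.1 brings it in within 24 hours. This is a fair reading. It shows that such outcomes are at risk of inconsistent reporting and are not excluded. It does not rescue the sentence: if the event is the pregnancy itself, the contraceptive-interaction case still contradicts 11.1.4 directly. Nor is it the obvious reading, since 11.3.2 speaks of what the event results in and calls this the pregnancy's serious outcome.

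The existing safeguards also stand. Pregnancies in female subjects within the stated period reach pharmacovigilance within 24 hours, and their outcomes follow on the pregnancy form. Section 11.2.6.2 requires suspected serious adverse drug reactions to be reported at once, however late they emerge.

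A reader might infer more than the documents support:

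- *Serious outcomes will be missing from the SAE tables.* Section 13.1.6.2 does not mention pregnancy. SAEs are recorded until 30 days after the last day of participation (11.2), and the treatment-emergent window in 11.1.6 closes 14 days after the last application. Many pregnancy outcomes would fall later than both, whatever 11.3.2 says.
- *The DSMB will not see them.* Sections 5.3 and 12 give the board aggregate safety data, and 5.3 adds concerns raised by investigators or the medical monitor. Nothing restricts its view to SAE forms.
- *Ending follow-up at delivery or termination is part of the error.* It contradicts nothing in the text. Longer infant follow-up would be a separate policy choice.
- *The programme's earlier pregnancies show missed cases or give a rate.* Section 11.3.2 lists 4 + 5 + 1 + 2 = 12. The rule covers all 5 spontaneous abortions, and nothing shows that the other 7 (4 normal births, 1 elective abortion, 2 lost to follow-up) met any criterion in 11.1.4. The protocol does not give the number of women at risk, so no frequency for this trial follows.

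**Conclusion.** Section 11.3.2 is wrong as written and should be reconciled with 11.1.4 and 11.2.6.1 in both texts. The contradiction over a suspected contraceptive interaction holds on any reading. The wider conflict, over hospitalized, life-threatening or otherwise serious outcomes, holds if 11.3.2 is taken at its word by a site that treats it as the governing section for pregnancy.

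The consequence is possible misclassification, with no SAE form and no stated deadline for an outcome that 11.1.4 calls serious. It is not a demonstrated loss of cases, and first notice of a pregnancy in a female subject is unaffected. The number of events concerned cannot be derived from the protocol. Sample size, power and the efficacy analysis are not touched.

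**What to change.** In Section 11.3.2 of both texts, replace the limiting sentence with wording such as: *A pregnancy or its outcome is an SAE if it meets any criterion in Section 11.1.4; spontaneous abortion and congenital anomaly are always reported as SAEs.* Then reword the sentence that follows so that the SAE Report Form and its 24-hour limit apply to every such outcome, in line with 11.2.6.1.

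The cost is two sentences in the next amendment. No visit, assessment or sample-size change follows. The Pregnancy Data Collection Form and the 24-hour notice of the pregnancy stay as they are.
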